14.3 Subject information and consent

It is the responsibility of the Investigator or designee to give each subject prior to inclusion in the study, full and adequate verbal and written information regarding the objectives and procedures of the study and the possible risks involved. The subjects must be informed about their right to withdraw from the study at any time. Written subject information should be given to each subject before enrolment. The written subject information must not be changed without prior discussion with CTC/the Sponsor. All subjects are required to provide informed consent prior to any study procedures. Furthermore, it is the responsibility of the Investigator or designee to obtain signed Informed Consent Form from all subjects prior to inclusion in the study.

The signed Informed Consent Form should be filed by the Investigator or designee for review by the Monitor. The Investigator will confirm receipt of the Informed Consent Form from each subject by signing the appropriate page of the Case Report Form.

14.4 Subject data protection

The Investigator should keep a subject identification list not to be available to the Sponsor, including sufficient information to link records, i.e. CRFs and hospital records. The subjects should be informed that the data will be stored and analyzed by computer, that Swedish and local regulations for the handling of computerized data will be followed and described in the written subject information and that identification of individual subject data will only be

possible for the Investigator. Furthermore, the subjects should be informed about the possibility of inspection of relevant parts of the records by representatives of CTC AB and/or Authorities.

14.5 Changes to the approved clinical study protocol

Any variation in procedure from that specified in the Final Study Protocol may lead to results of the trial being questioned and in some cases rejected. Any proposed protocol change must therefore be discussed with and approved by the Sponsor and submitted for Independent Ethics Committee approval or notification. Any protocol change should be documented in a Protocol Amendment.

14.6 Audits and inspections

Authorized representatives of Sponsor or an IEC may perform audits or inspections at the research clinic, including source data verification (SDV). The purpose of an audit or inspection is to systematically and independently examine all study-related activities and documents, to determine whether these activities were conducted, and data were recorded, analyzed, and accurately reported according to the protocol, ICH-GCP guidelines and any applicable regulatory requirements.

14.7 Insurance

The Sponsor is liable under law and in accordance with generally accepted standards for unexpected injuries, including death, that the use of the study drug may cause subjects.

The Sponsor will indemnify and hold the Investigator as well as any hospital, institution, ethics committee or the alike, harmless from any claims for damages caused by such injuries but only to the extent that the claim is not caused by gross negligence or failure to comply with the protocol and/or governmental regulation by the indemnified.

The Sponsor will require the Investigator to indemnify and hold the Sponsor harmless from any claim caused by gross negligence and/or failure to comply with the protocol and/or governmental regulation by the Investigator.

The Investigator agrees to notify the Sponsor whenever he becomes aware of a claim or action and to co-operate with and authorize the Sponsor to carry out sole management of such claim or action.

The Sponsor's responsibility is covered by product liability insurance. The insurance also covers the Sponsor's liability under law and generally accepted liability standards within industry toward any third parties, including subjects, as Sponsor of the Study. The Investigator's responsibility is covered by liability insurance for scientific studies in human subject. CTC has a company insurance covering services performed by CTC.

15 STUDY MANAGEMENT

15.1 Training of study site personnel

Before enrolment of the first study subject a Sponsor representative or delegate will perform a study initiation visit at the research clinic. The requirements of the CSP and related documents will be reviewed and discussed and the investigational staff will be trained in any study specific procedures and system(s) utilized.

It is the responsibility of the Investigator to ensure that all personnel involved in the study are fully informed of all relevant aspects of the study, including detailed knowledge of and training in all procedures to be followed.

Curriculum vitae will be collected from all personnel and be kept in the Trial Master File.

15.2 Clinical monitoring

The study site will be monitored periodically during the study, as agreed with the Investigator. The Monitor will ensure that all aspects of the protocol are followed, including the randomization procedure, the accurate recording of results, the reporting of Adverse Events, Product Accountability and record keeping.

Furthermore, it will be verified that the clinical facilities remain accurate, and that the Case Report Forms are in agreement with source data. For this purpose, the Monitor will be given access to hospital records, original laboratory data, etc., as far as they relate to the study, without jeopardizing subject integrity and as agreed with the Investigator prior to the study. Case Report Forms for all included subjects will be made available to the Monitor for review and collection as agreed with the Investigator. It is important that the Investigator and other relevant personnel are available during the monitoring visits and possible audits and that sufficient time is devoted to the process

15.3 Source data document

Monitoring visits will be made during the trial, to ensure that all aspects of the protocol are followed. Source documents will be reviewed for verification of agreement with data on CRFs.

A separate *Source Data Verification List* will be generated before start of enrolment, specifying the location of the source of derived information appearing in the CRF. This document must be signed by the Principal Investigator and the Monitor to confirm agreement before start of recruitment.

The Investigator should guarantee access to source documents to the Monitor and the IECs, if required.

15.4 Study agreements

The Principal Investigator must comply with all the terms, conditions, and obligations of the Clinical Study Agreement for this study.

Agreements between Sponsor and CTC must be in place before any study-related procedures can take place, or subjects be enrolled.

15.5 Study time table and end of study

Ethics committee application will be submitted in October 2017. Performance of clinical part of study is expected to be finished in the beginning of 2018.

The end of the clinical part of the study is defined as the last visit of the last subject participating in the study.

15.6 Discontinuation of the study

The Sponsor reserves the right to discontinue the study prior to inclusion of the intended number of subjects, but intends only to exercise this right for valid scientific or administrative reasons. After such a decision, the Investigator must call in all participating subjects. At this visit, all delivered unused study products and other study materials must be collected and all CRFs be completed as far as possible.

15.7 Reporting and publication

15.7.1 Clinical study report

A summarizing report should be submitted to the applicable IEC within 12 months after completion of the study.

A clinical study report (CSR), in compliance with ICH E3; *Structure and content of clinical study reports*, describing the conduct of the study, *the statistical analysis performed* and the results obtained, will be prepared by CTC. The report will be reviewed and approved by, as a minimum, the Principal Investigator, the Statistician and the Sponsor.

15.7.2 Confidentiality and ownership of study data

All information not previously published concerning the test product and the Sponsor's research, including patent applications, manufacturing processes, basic scientific data, etc., is considered confidential and should remain the sole property of the Sponsor. The Investigator agrees to use this information only in connection with this study and will not use it for other purposes without the written permission from the Sponsor.

15.7.3 Publication

It is agreed that the Sponsor has the ownership of all results. Before publication, if publication is agreed upon, the Sponsor will be given the opportunity to review and comment upon the manuscript. The time for review should not exceed 30 days after receipt of the manuscript. If the Investigator has not submitted the results for publication within 6 months after completion of the final CSR, the Sponsor will have the right to publish. In this case the Investigator will be given 30 days to review and comment on the manuscript prior to submission to the publisher.

15.8 Archiving

To enable any further evaluations and/or audits from Health Authorities/the Sponsor, the Investigator agrees to keep records, including the identity of all participating subjects, all original signed Informed Consent Forms, copies of all CRFs and detailed records of drug

disposition. To comply with international regulations, the records should be retained by the Investigator for 15 years.

16 DATA MANAGEMENT

16.1 Case report form

Data will be collected in CRFs specifically designed for this study. The Investigator or an authorized person will record subject data in the CRF in a precise and accurate manner. Abbreviations should not be used. The Investigator is responsible for the data entered and will sign off the CRF at the end of the study. The data should be recorded as soon as they are generated. CRF entries must be made with an archive resistant pen. Any correction should be marked with a single bar through the error and the correct information should be written next to it. All corrections must be initialed and dated. Correction fluid must not be used. Only persons authorized by the Investigator are allowed to make entries to the CRF.

16.2 Database management plan and database design

Detailed information on data management will be described in a study-specific DMP.

The person entering data into the database is not allowed to attempt any personal interpretation or to make any decisions on the data other than self-evident corrections as listed in the study-specific Data Entry Instructions or Data Handling Report. Single data entry type will be applied.

Data validation/data cleaning procedures are designed to assure validity and accuracy of clinical data. These procedures consist of manual reviewing during data entry and computerized edit checks and queries for identifying data values that are outside the allowed range, protocol violations, incomplete or inconsistent. The Data Validation Plan (DVP) specifies the checks that are to be performed on subject data for the study. All study-specific and standard data validation programming will be tested in a separate testing environment prior to use on production data.

16.3 External data

External data consists of data that is not recorded in CRFs. Data may be received in electronic format or paper printout. Key variables are defined in order to uniquely identify each sample record. File and data formats are agreed with the external data provider. Any electronically transferred data must contain origin, date created, date sent and number of records at minimum.

16.4 Medical encoding

Medical encoding will be done by trained personnel at CTC. AEs and medical history verbatim terms are encoded using the Medical Dictionary of Regulatory Activities (MedDRA), latest version available when approving the DMP.

Prior and concomitant medications will be coded according to the WHO Anatomic Therapeutic Chemical (ATC) classification system.

All coding will be approved by CTC.

CONFIDENTIAL	39 (45)
--------------	---------

16.5 Database lock

When all data have been entered, discrepancies solved the database will be locked and the data will be analyzed.

17 STATISTICAL METHODS AND DETERMINATION OF SAMPLE SIZE

The following is an outline of the statistical methodology that will be used to analyze this study. A more detailed description will be provided in a separate statistical analysis plan (SAP) that may also include additional exploratory analyses not explicitly mentioned in the following sections. The SAP will be finalized before closure of the study database and deviations from the SAP will be reported and justified in the clinical study report.

17.1 General

Continuous data will be presented using summary statistics. Data will be presented in terms of number (N), arithmetic mean, standard deviation (SD), minimum and maximum value.

Categorical data will be presented as counts and percentages. When applicable, summary data will be presented by treatment, and by assessment time. Individual subject data will be listed by subject number, treatment, and, where applicable, by assessment time.

A significance level of 5% with two-sided tests will be used in all comparisons.

The test articles below will in all analyses be compared to the reference product.

Any comparisons between the test articles will be described in the SAP.

Test articles:

1= ZYN Smooth containing 3 mg nicotine per portion

2= ZYN Smooth containing 6 mg nicotine per portion

3= ZYN Smooth containing 3 mg nicotine per portion (alternative manufacturing process)

4= ZYN Smooth containing 6 mg nicotine per portion (alternative manufacturing process)

Reference articles:

5= Swedish portion snus PSWL 1.0 g (8 mg nicotine/g)

17.2 Determination of sample size

The primary endpoint is nicotine extraction. The study will include 18 subjects. A previous study [Lunell E & Curvall M 2011] has made the calculation of sample size possible. Nicotine extraction from a 1 g Swedish portion snus (PSWL) containing 8mg nicotine/pouch was estimated at 2.18 ± 0.92 mg per portion. Under the assumption of a complete dissolution and *in-vivo* extraction of the 3 and 6 mg ZYN® products, respectively, versus the 2.18 ± 0.92 mg nicotine, and a standard deviation of 5.0 the estimated sample size is 16 with a power of 80% and alpha=0.05. The randomization will be performed using Latin Squares approach.

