8 STUDY OBJECTIVES AND ENDPOINTS

8.1 Primary objective(s)

To compare each subject's AUC_{inf} based on plasma concentrations of nicotine after administration of one single dose of a novel, non-tobacco-based nicotine pouch containing 3 and 6 mg of nicotine, to that of one single dose from a 1 g Swedish snus pouch containing 8 mg of nicotine.

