8.1.1 Primary endpoint (s)

 AUC_{inf} based on plasma concentrations of nicotine after administration of one single dose of a novel, non-tobacco-based nicotine pouch containing 3 and 6 mg of nicotine, to that of one single dose from a 1 g Swedish snus pouch containing 8 mg of nicotine.

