8.2 Secondary objectives

- 1. To compare AUC_{60min} , C_{max} , T_{max} , AUCo-t and terminal half-life of a novel, non-tobacco-based nicotine pouch to that of a Swedish snus pouch.
- 2. To compare the estimated *in-vivo* extracted amount of nicotine from a novel, non-tobacco-based nicotine pouch containing 3 and 6 mg of nicotine, respectively, with that from a 1 g Swedish snus pouch containing 8 mg of nicotine.
- **3.** Comparison of pulse rate and subjective effects ("head buzz") after study product administration (proxy for *in vivo* nicotine uptake).
- 4. Adverse events
- 8.2.1 Secondary endpoints
 - 1. AUC_{60min}, C_{max}, T_{max}, AUCo-t and terminal half-life of a novel, non-tobacco-based nicotine pouch to that of a Swedish snus pouch.
 - 2. In-vivo extracted amount of nicotine
 - 3. To assess the correlation between the estimates of AUC(inf) and the total amount of nicotine extracted from the ZYN® pouches.
 - 4. Pulse rate and VAS for measure "head buzz" (head rush, "hit", feeling alert, overall "product strength"), using a 100-mm visual analogue scale (VAS) anchored with "not at all" to "extremely" at preset time points up to 60 minutes (predose, + 5min, +10 min, +15 min, +30 min, +60 min after each dose), respectively, after study product administration (proxy for systemic uptake).
 - 5. Collection of adverse events

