17.5 Analysis of primary endpoint

AUC_{inf} based on plasma concentrations of nicotine after administration of one single dose of a novel, non-tobacco-based nicotine pouch containing 3 and 6 mg of nicotine, to that of one single dose from a 1 g Swedish snus pouch containing 8 mg of nicotine will be described using summary statistics and non-parametric signed Wilcoxon rank sum test for within subject difference.

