17.6 Analysis of secondary endpoints

The mean + SD extracted dose of nicotine from each pouch, will be calculated. The extracted dose of nicotine will be analyzed using the signed Wilcoxon rank sum test and Students t-test for within subject difference. The correlation between the AUC and the total amount of nicotine extracted from the pouch will be analyzed using Proc corr. in SAS.

The mean + SD of AUCinf based on plasma concentrations of nicotine after administration of of each pouch, will be calculated. AUC60min, Cmax, Tmax, AUCo-t and terminal half-life will also be calculated.

AUC60min, Cmax, Tmax, AUCo-t and terminal half-life of a novel, non-tobacco-based nicotine pouch to that of a Swedish snus pouch will be described using summary statistics and analyzed using signed Wilcoxon rank sum test for within subject difference.

Pulse rate and VAS for measure of subjective "head buzz" (head rush, "hit", feeling alert, overall "product strength"), will be summarized by treatment and period using descriptive statistics.

The intra subject difference of pulse rate will be analyzed using the signed Wilcoxon rank sum test and Students t-test for within subject difference.

The intra subject difference of VAS scales for "head buzz" (head rush, "hit", feeling alert, overall "product strength") will be analyzed using the signed Wilcoxon rank sum test and Students t-test for within subject difference.

All AE data will be fully listed by Investigator terms and MedDRA Preferred Term (PT). AE data will be summarized by System Organ Class (SOC) and PT.

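### Section 17.2 names nicotine extraction as the primary endpoint and sizes the trial on it, while the rest of the protocol makes AUCinf primary, so the stated 80% power is not power for the primary endpoint

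*Protocol*

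**What the plan says.** **AUCinf as primary.** The primary objective in Section 8.1 (also in the synopsis) reads "To compare each subject's AUC_{inf} based on plasma concentrations of nicotine after administration of one single dose of a novel, non-tobacco-based nicotine pouch", set against snus. Section 8.1.1 gives the primary endpoint as "AUC_{inf} based on plasma concentrations of nicotine after administration of one single dose". Section 17.5, headed as the analysis of the primary endpoint, says that AUCinf "will be described using summary statistics and non-parametric signed Wilcoxon rank sum test for within subject difference".

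**Extraction as secondary.** The extracted amount is secondary objective 2 in Section 8.2 and secondary endpoint 2 in Section 8.2.1. Section 17.6, on secondary endpoints, says: "The extracted dose of nicotine will be analyzed using the signed Wilcoxon rank sum test and Students t-test for within subject difference".

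**Extraction as primary.** Section 17.2 states: "The primary endpoint is nicotine extraction. The study will include 18 subjects". Its inputs are all extracted milligrams. Extraction from the 1 g snus pouch "was estimated at 2.18 ± 0.92 mg per portion", the 3 and 6 mg pouches are assumed to be fully extracted, and the SD is 5.0. The result is 16 subjects for 80% power at alpha 0.05. The statistical methods paragraph of the synopsis repeats this calculation, without the sentence naming the primary endpoint, in the same synopsis that gives AUCinf as the primary objective.

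**The concern.** The opening sentence of Section 17.2 cannot be true together with Sections 8.1, 8.1.1 and 17.5. It is also more than a stray label, because the whole calculation follows it: means, SD, sample size and power all concern extraction. The only power figure in the protocol therefore belongs to an endpoint that the objectives rank as secondary.

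What is at stake is the justification of the sample size. A reader who takes the 80% at face value will think it describes the AUCinf comparison. Nothing in the protocol says how precisely 18 subjects will estimate the AUCinf ratio, or what difference they could detect. A study report would also have to cite one section of the protocol against another when it states what the trial was designed to detect.

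**Working it through.** **1. Reproducing the plan's figure.** Inputs from Section 17.2: snus mean 2.18 mg, test means 3 and 6 mg, SD 5.0, power 80%, alpha 0.05. Section 17.1 makes tests two-sided. The section does not name the test, so a paired t-test with 5.0 as the SD of the within-subject difference is tried.

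- 6 mg versus snus: difference 6 − 2.18 = 3.82; standardised 3.82/5.0 = 0.764. The required n is 15.5, rounded up to 16. Power is 81.5% at 16 and 86.3% at 18. (The normal approximation ((1.96 + 0.84) × 5.0/3.82)² gives 13.4, rounded up to 14.)
- 3 mg versus snus: difference 3 − 2.18 = 0.82; standardised 0.82/5.0 = 0.164. The required n is about 294. Power is 9.4% at 16 and 10.1% at 18.

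So the 16 is an extraction figure, and it fits only the 6 mg comparison. Section 17.2 presents it as covering both strengths.

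**2. The SD.** The SD of 5.0 stands unexplained beside the quoted 0.92. If 0.92 were the SD of the difference, the 3 mg comparison would need about 12 subjects (standardised 0.82/0.92 = 0.89; n = 11.9). The choice of SD therefore decides whether the 3 mg comparison is adequately powered.

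**3. Power for AUCinf.** It cannot be computed from the protocol, which gives no AUCinf mean, difference, ratio or variance. What can be stated without further inputs is the standardised within-subject difference detectable with 80% power by a paired t-test: 0.70 at 18 subjects and 0.75 at 16. For a signed-rank test, at an assumed relative efficiency of 0.955, these become about 0.72 and 0.77.

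**4. Illustration on the ratio scale.** The within-subject CVs are assumptions, not protocol figures. For one test product against snus on log AUCinf:

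- within-subject log SD s = √ln(1 + CV²), and SD of the difference = s√2, which is 0.280, 0.415 and 0.545 for CV 20%, 30% and 40%
- 95% CI factor = exp(t × s√2/√n), with t = 2.110 (n = 18, df 17) or 2.131 (n = 16, df 15)
- ratio detectable with 80% power = exp(−0.70 × s√2) at n = 18 and exp(−0.75 × s√2) at n = 16
- power at a true ratio of 0.80: noncentral t with standardised difference 0.223/(s√2), where 0.223 = −ln 0.80

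| | CV 20% | CV 30% | CV 40% |
|---|---|---|---|
| CI factor, n = 18 | 1.15 | 1.23 | 1.31 |
| CI factor, n = 16 | 1.16 | 1.25 | 1.34 |
| Detectable ratio, n = 18 | 0.82 | 0.75 | 0.68 |
| Detectable ratio, n = 16 | 0.81 | 0.73 | 0.66 |
| Power at ratio 0.80, n = 18 | 89% | 58% | 37% |
| Power at ratio 0.80, n = 16 | 85% | 52% | 34% |

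The signed-rank test planned in Section 17.5 would do slightly worse.

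**The case against.** The strongest reply is that the protocol does not really waver. The synopsis objective, 8.1, 8.1.1 and 17.5 all agree on AUCinf, extraction is consistently secondary in 8.2.1 and 17.6, and one sentence in 17.2 disagrees. The synopsis version of the same paragraph leaves that sentence out. This stands: it is one wrong sentence against an otherwise consistent designation. But correcting that sentence alone would leave a power claim with no link to AUCinf.

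Section 7.1 describes the main aim as covering both extraction and the resulting uptake, so one could argue that power for extraction carries over to AUCinf. The protocol makes no such argument. Sections 8.2.1 and 17.6 treat the correlation between the two as a question to be studied, and an SD in extracted milligrams says nothing about the variability of AUCinf.

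Two stronger readings are tempting, and the protocol supports neither. A reader might infer that success could be claimed on whichever endpoint turns out favourable. The protocol defines no success criterion or margin, 17.5 names one primary endpoint, and 17.7.3 says conclusions should not rest on significance alone. A reader might also infer that the trial is underpowered for AUCinf. That cannot be shown without an AUCinf effect and variance.

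The gap between a t-type calculation and the planned signed-rank test is small and is not part of the defect. Nor does a separate SAP settle the matter, because the contradiction lies within the protocol.

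**Conclusion.** The point holds as an internal inconsistency. Section 17.2 misnames the primary endpoint, and the 80% power stated there and in the synopsis is not power for AUCinf. Power for AUCinf is undocumented: at 18 subjects and a true ratio of 0.80 it runs from 89% to 37% as the assumed CV goes from 20% to 40%, which lies on both sides of 80%. Those figures rest on assumed CVs and a paired log-scale comparison.

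The extraction calculation does not support 80% power for both strengths either. On its own inputs, and reading 5.0 as the SD of the within-subject difference, it supports 6 mg versus snus; the 3 mg comparison has about 10% power at 18 subjects.

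**What to change.** - In Section 17.2, name AUCinf as the primary endpoint.
- In Section 17.2 and in the statistical methods paragraph of the synopsis, stop presenting 80% as power for the primary endpoint. State instead the expected CI width or the detectable ratio for AUCinf at 18 and at 16 subjects, under a stated within-subject CV with its source.
- If the extraction calculation is kept, label it as supporting the secondary endpoint and as applying to 6 mg versus snus only. Explain or correct the SD of 5.0 against the quoted 0.92.

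The cost is protocol wording in two places and one sourced CV. The number of subjects, the assessments and the planned tests do not change.

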Subjective effects – Each subject's rating of product "strength" using a Visual Analogue Scale (VAS): (head "buzz", "head rush", "hit", feeling alert, overall "product strength"), anchored with "not at all" to "extremely". VAS scores will be obtained at the following time points before (0), 5, 10, 15, 30 and 60 minutes after each product is administered.

Safety assessments

Adverse Events will be collected starting with administration of the Investigational Product until the last follow-up from the first dose.

Statistical methods

The study will include 18 subjects. A previous study (Lunell E & Curvall M 2011) has made the calculation of sample size possible. Nicotine extraction from 1 g Swedish portion snus containing 8 mg nicotine/pouch was estimated at 2.18 ± 0.92 mg per 1 g portion. Under the assumption of a complete dissolution and extraction of the 3 and 6 mg ZYN® products, respectively, versus the 2.18 ± 0.92 mg nicotine, and a standard deviation of 5.0 the estimated sample size is 16 with a power of 80% and alpha=0.05.

3 TA	BLE OF CONTENTS	
2 STU	UDY SYNOPSIS	4
3 TA	BLE OF CONTENTS	7
4 LIS	T OF ABBREVIATIONS AND DEFINITIONS OF TERMS	11
5 IMI	PORTANT MEDICAL PROCEDURES TO BE FOLLOWED BY THE	
	INVESTIGATOR	
5.1	Medical emergencies contacts	13
	Overdose	
6 INV	/ESTIGATOR(S) AND STUDY ADMINISTRATIVE STRUCTURE	
6.1	.1 Investigational Product manufacturing and packaging	15
6.1		
7 INT	RODUCTION	16
7.1	Project background	16
7.2	Investigational products	17
7.2	2.1 Product characteristics	17
7.3	Risk/benefit assessment	17
7.3	S.1 Summary of risk management	17
8 STU	UDY OBJECTIVES AND ENDPOINTS	18
8.1	Primary objective(s)	18
8.1	.1 Primary endpoint (s)	18
8.2	Secondary objectives	18
8.2	2.1 Secondary endpoints	18
9 INV	/ESTIGATIONAL PLAN	19
9.1	Overall study design and schedule of events	19
9.2	Rationale for study design and dose groups	21
10 ST	CUDY POPULATION	21
10.1	Recruitment	21
10.2	Screening and enrolment log	21
10.3	Number of subjects	21
10.4	Inclusion criteria	21
10.5	Exclusion criteria	22
10.6	Restrictions during the study	22
10.7	Criteria for subject withdrawal	23
10.	7.1 General withdrawal criteria	23
10.	7.2 Procedures for discontinuation of a subject from the study	23
CONFI	DENTIAL 7 (45)	

10.7	.7.1 Subject replacement	23
10.8	Randomization	24
10.9	Blinding	24
11 TR	REATMENTS	24
11.1	Identity of investigational products	24
11.2	Packaging and labelling	24
11.3	Conditions for storage	24
11.4	Dispensing and accountability	24

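### The stated n = 16 at 80% power holds only for the 6 mg pouches; on the same inputs the 3 mg comparison has about 9% power, and the SD of 5.0 contradicts the assumptions beside it

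*Protocol*

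**What the plan says.** Protocol section 17.2 takes its reference value from a previous study, in which snus extraction "was estimated at 2.18 ± 0.92 mg per portion". It then assumes complete "extraction of the 3 and 6 mg ZYN® products, respectively, versus the 2.18 ± 0.92 mg nicotine" and, with "a standard deviation of 5.0 the estimated sample size is 16 with a power of 80% and alpha=0.05", arrives at one sample size. The synopsis (Statistical methods) repeats the calculation: "Under the assumption of a complete dissolution and extraction of the 3 and 6 mg ZYN® products, respectively, versus the 2.18 ± 0.92 mg nicotine", with the same SD and the same 16. The planned number is 18.

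Section 17.1 has all four test articles (two of 3 mg, two of 6 mg) compared with snus, and fixes the sidedness: "A significance level of 5% with two-sided tests will be used in all comparisons". Section 17.6 analyses extracted dose by a signed-rank test and a paired t-test on within-subject differences. Nothing limits the 80% to the 6 mg products. The SD of 5.0 has no unit and no source, and the text does not say whether it belongs to one product or to a difference.

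**The concern.** Two doses measured against one reference mean give two different effect sizes, so one sample size cannot carry 80% power for both unless it is driven by the smaller difference. Here it appears to be driven by the larger. The SD of 5.0 also stands next to a cited SD of 0.92 and an assumption of complete extraction, and neither leads to it.

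Section 17.2 is the protocol's only statement of power. If it is wrong for the 3 mg pouches, two of the four test products are presented as adequately powered when, on the stated inputs, they are not. A non-significant 3 mg result could then be taken as evidence of similarity to snus.

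**Working it through.** **Inputs.** Snus mean 2.18 mg and SD 0.92 mg, complete extraction (3 mg or 6 mg), SD 5.0, alpha 0.05 and power 80% (all section 17.2); two-sided tests (17.1); within-subject comparison by paired t-test (17.6); planned n 18 (10.3, 17.2). I take 5.0 to be in mg and to be the SD of the within-subject difference, because that reading reproduces the stated 16.

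**Differences.**
- 3 mg: 3 − 2.18 = 0.82 mg
- 6 mg: 6 − 2.18 = 3.82 mg

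**Formula.** Paired t-test power from the noncentral t distribution with n − 1 degrees of freedom and noncentrality (d / SD) × √n, two-sided 5%.

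**Reproducing the stated figure (6 mg, SD 5.0).** d / SD = 3.82 / 5.0 = 0.764. At n = 16 the noncentrality is 0.764 × 4 = 3.056. Power is 78.6% at n = 15 and 81.5% at n = 16, so 16 is the smallest n that reaches 80%. At n = 18 it is 86.3%.

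**Same inputs, 3 mg.** d / SD = 0.82 / 5.0 = 0.164. At n = 16 the noncentrality is 0.164 × 4 = 0.656. Power is 9.4% at n = 16 and 10.1% at n = 18; 80% needs n = 294. Other methods do not rescue it with SD 5.0: the paired normal approximation gives 292, one-sided paired versions 230 to 232, a two-sample comparison 584 per arm, and a cross-over formula 146 per sequence.

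**Is 5.0 compatible with the other inputs?**
- Under complete extraction each ZYN value is a constant (3 or 6 mg), so the SD of the difference equals the snus SD, 0.92.
- Without that assumption, an amount between 0 and 6 mg has an SD of at most 3 mg, and one between 0 and 3 mg at most 1.5 mg. The SD of a difference cannot exceed the sum of the two SDs: 3 + 0.92 = 3.92 mg (6 mg pouch) or 1.5 + 0.92 = 2.42 mg (3 mg pouch). Both are below 5.0.

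**Power across SDs of the difference (two-sided paired t).** The value 1.30 is an assumption: ZYN extraction also has SD 0.92 and is uncorrelated with snus, so 0.92 × √2 = 1.30.

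| SD | 3 mg: n for 80% | 3 mg: power at 16 | 3 mg: power at 18 | 6 mg: n for 80% |
|---|---|---|---|---|
| 5.0 | 294 | 9.4% | 10.1% | 16 |
| 1.30 | 22 | 65% | 71% | 4 |
| 0.92 | 12 | 91% | 95% | 3 |

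The difference detectable with 80% power at n = 18 is 3.5 mg if the SD is 5.0 and 0.64 mg if it is 0.92.

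**The case against.** The strongest reply is that the 9% rests on an SD that is itself untenable. With 0.92 in its place, 18 subjects give 95% power for the 3 mg comparison, so the two errors partly offset and no one is short of subjects. That stands: the trial is not shown to be too small for extraction. But the 0.92 result is the favourable end. It treats ZYN extraction as free of variation, and it borrows an SD from 30 minutes of use (section 9.2) for a trial with 60 minutes of use. At SD 1.30 the 3 mg power at 18 falls to 71%. Whether the 3 mg comparison is powered therefore depends on the one input that has no source.

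A second reply is that the harm is conjectural. The protocol sets no similarity criterion, section 17.7.3 promises clinical judgement alongside significance tests, and sections 8.1 and 17.5 make AUCinf primary, with extraction secondary. This limits the consequence. It does not make the power statement true, and section 17.2 itself calls extraction the primary endpoint. That conflict is a separate matter, and it means the protocol gives no power for AUCinf.

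A third reply is that comparing 5.0 with the maximum SD of one bounded product is not enough, because the relevant SD is that of a difference. That is right, and it is why the bound above adds the snus SD. The conclusion is unchanged.

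**Conclusion.** The concern holds; the sample-size statement is wrong as written. On the protocol's own inputs, "the estimated sample size is 16 with a power of 80% and alpha=0.05" is correct for the two 6 mg products (81.5%) and wrong for the two 3 mg products (9.4% at 16, 10.1% at 18, 294 needed). Separately, 5.0 cannot be the SD of the difference in mg given complete extraction, which implies 0.92, nor given bounded extraction with a snus SD of 0.92, which caps it at 3.92 or 2.42.

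This rests on a two-sided paired t-test, nominal pouch contents, and 5.0 being in mg and referring to the within-subject difference. The first conclusion does not depend on the choice of method: no variant tried gives 16 for 3 mg with SD 5.0. The finding is that the justification is incoherent, not that 18 subjects are too few.

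**What to change.** Keep 18 subjects. In section 17.2 and the synopsis:

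- State the assumed difference and the power at n = 18 separately for 3 mg and 6 mg against snus.
- Replace 5.0 with an SD of the within-subject difference. Give its unit and source, and make it consistent with the extraction assumption. If the source leaves a range, show the power across it.
- If 5.0 is nevertheless kept, justify it, say that the 80% applies to the 6 mg comparison only, and state that the 3 mg comparison has about 10% power.

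The cost is a change of protocol wording in two places: no added subjects, visits or procedures. If 5.0 stays, a stated figure becomes less favourable.
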